### 13.3.2. Nutritional intake

Information related to nutritional intake will be gathered from the EMR including goal calories, actual calories consumed, and the amount of dietary fiber consumed in grams. All ICU patients at our institution receive a complete clinical nutritional assessment with calculation of goal calories based on the Penn State Equation with the modified equation used for individuals >60 years old or those with BMI >30 as described by Frankenfeld *et al.* in 2009. Actual calories and grams of fiber consumed will be based on the specific components of the tube feeds received or, among patients on an *ad lib* diet, the food consumed. The nutritional components of all CUMC diets are completely specified in terms of calories, fat, protein, carbohydrate, and fiber content. To calculate calories and fiber consumed, the study team will refer to the proportion of each meal consumed as recorded by ICU nurses and to the volume of tube feeds delivered which is captured hourly in the EMR. In those receiving tube feedings, the interval number of tube feeding interruptions will be recorded at each assessment or recorded as 0 in those receiving *ad lib* diets.

### 13.3.3. Long-term telephone follow-up

Telephone interviews will be conducted with subjects or their surrogates 3 months after ICU admission and again 6 months after ICU admission. In the event that subjects are still hospitalized, these interviews will be conducted at the bedside. Vital status will be ascertained and, to minimize loss of follow-up information, we will interview subjects or surrogates to determine (1) discharge location type (classified as home, short-term rehabilitation, or long-term rehabilitation including skilled care facilities), (2) hospital admission to non-CUMC facilities after ICU discharge, (3) physician office visits after ICU discharge, and (4) infections or other adverse events after ICU discharge. If there are non-CUMC hospital admissions or other healthcare

interactions, permission will be requested to obtain relevant records to determine the nature of infections and to assess for potential medium- to long-term AEs related to the study intervention. Among surviving subjects, the EQ-5D-5L (EuroQol 2009) will be used to determine health status across the domains of mobility, self-care, activity levels, pain, and anxiety/depression. Use of this highly validated instrument will facilitate standardization and generalizability of results and will provide preliminary data for post-ICU discharge monitoring for later phase trials. This instrument can be applied via telephone in 5 minutes and was recommended in 2017 for post-ICU assessment of overall well-being after a three-round modified Delphi process involving clinical researchers from over 16 countries, patients/caregivers, clinicians, and research funders. EQ-5D-5L responses have the potential to vary depending on whether answers are provided on patients versus surrogates, and therefore we will additionally assess post-ICU disability using Katz' Index of Independence in ADLs (Activities of Daily Living). Although focused on functional status rather than well-being, Katz' ADLs has been validated as an important patient-centered outcome across dozens of populations and unlike the EQ-5D-5L has high agreement between patients and caregivers.

#### **14. Data collection and management**

The Columbia DCC will oversee use of a custom-designed, REDCap-based clinical trial data management system. REDCap is a widely used web-based relational data system developed at Vanderbilt University with NIH support to collect research information in 21CRFPart11, FISMA and HIPAA-compliant environments. REDCap functionality that will be used in this trial include randomization, subject scheduling, *ad hoc* reporting, data verification and audit trails. Paper CRFs will be used to collect bedside data, while readily available selected electronic data (e.g., laboratory values) will either be directly “pulled” from Columbia clinical servers and merged into the REDCap database or manually entered into REDCap. REDCap ‘Events’ will be specified corresponding to the study assessment timepoints: baseline, Days 3, 7, 14, 30, 3 months, and 6 months. Data of each type will be associated in the system with the appropriate time period. REDCap “Anytime” functionality will be used to capture adverse events and other incidents that can occur at any time, i.e. events that are not associated with fixed time periods. The REDCap system has built-in data verification aspects that will be utilized for the trial including minimum and maximum ranges and other logical checks, and automatic checks for completion of individual items and forms.

##### 14.1. Data security within REDCap

The servers on which DCC REDCap project data are stored are located in a physically and electronically secure environment maintained by institutional IT staff on the CUMC campus. The DCC confirms project data access privileges on a monthly basis, and REDCap requires strong passwords, which must be changed periodically. In this trial, to ensure data security, explicit identifiers needed for recruitment and scheduling (names, addresses, phone numbers, email addresses, medical record numbers) will be maintained separately and will *not* be stored in the REDCap database.

##### 14.2. Record retention

All electronic and paper records will be retained for a minimum of 6 years from the trial end date in accordance with New York State law and meeting or exceeding Federal minimums. Consent forms, CRFs, and other relevant paper documents will be moved to secure longterm paper storage once the trial has been closed and the data locked. Record retention will be prolonged beyond 6 years as necessary if required by the funding agency.

#### **15. Safety and adverse events (AEs)**

Adverse health events, laboratory irregularities, and even death are expected in ICU patients with sepsis and it would be difficult or impossible to accurately document and label all adverse health events. This is a common problem faced by ICU trials. The solution recommended by academic critical care research groups (e.g., Cook *et al.*) is to pre-specify AEs of interest for careful monitoring. In keeping with this approach, this study will produce detailed reports of these AEs for the DSMC at standard intervals while only unanticipated problems that also meet criteria for serious adverse events (SAEs) will be reported to the DSMC in real time. AEs will be reported for all individuals who have received one or more doses of the intervention. This study has pre-specified AEs in the following categories.

- Bloating: graded 0-3 based on patient report: patient mean and maximum values will be reported;
- Stool consistency and frequency: graded 0-4 for consistency and with an integer denoting frequency over 24 hours based on nursing report. For each patient, mean and maximum values will be reported;
- Electrolyte imbalances: For each patient, the minimum and maximum values for serum calcium, magnesium, phosphate, potassium, and sodium will be reported. This will be done for the 7 days of the intervention period and separately from Day 7 through Day 30/discharge;
- Gastrointestinal AEs: the gastrointestinal AEs of nausea, vomiting, bowel obstruction, and abdominal pain will be recorded as present or absent for each assessment and separated from other AEs to improve early pattern recognition by the DSMO;
- Infections: Infections are both an AE and an outcome and will be adjudicated as previously described. For each infection, the date of the infection, suspected site, organism, and antibiotics received will be recorded. Infections will be further classified as MDR vs non-MDR using the criteria previously described;
- Death: death will be gathered from the hospital EMR, which interfaces with the social security death index.

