### 10.3. Additional outcomes:

10.3.1. *Feasibility.* Descriptive demographic and clinical data will be compared across study groups to assess adequacy of randomization. Summary statistics (count data) will be recorded for patients across all 3 intervention arms to assess feasibility as (1) the enrollment rate (enrolled)/(enrolled+refusals) over each 12 month period; (2) protocol adherence (proportion of randomized subjects who receive 1 or more doses of the allocated intervention); and (3) fidelity of the intervention (defined as the proportion of high/low inulin allocated vs received and also categorically as receipt of 90% or more allocated doses of inulin across groups). Feasibility goals are as stated in Aim 1.

10.3.2. *Rates of pre-specified AEs.* There will be active ascertainment of AEs in the following categories, which will be compared between intervention groups. This will be done through the end of the intervention period (ICU Day 7) and also through Day 30/discharge to assess for delayed AEs.

- Stool frequency, measured by subject or nursing report by the number of spontaneous stools over the 24 hours preceding each assessment;
- Stool consistency, measured by subject or nursing report as an ordinal variable (0-4) over the 24 hours preceding each assessment;

- Abdominal bloating, measured by subject or nursing report as an ordinal variable (0-3) over the 24 hours preceding each assessment.
- Electrolyte abnormalities, measured by examining for differences in median values, minimum/maximum values, and proportions of values outside the normal range. This will be done for glucose, calcium, magnesium, phosphate, potassium, and sodium.
- Nausea, vomiting, obstruction, and abdominal pain. These will be recorded as present or absent based on bedside assessment of the subject or based on the nursing impression.
- Culture-proven infections, which will be considered both an AE and an outcome (see 10.3.4).

10.3.3. *Antibiotic resistance gene fraction on ICU Day 3.* DNA will be extracted from rectal swabs (MoBio PowerFecal, Carlsbad, CA) and assessed using multiplex quantitative PCR (Qiagen Cat. No. 330261, Valencia, CA) for 87 common antibiotic resistance genes. Within-individual differences in multiplex qPCR results will be compared from baseline to Day 3 both as summed changes and within relevant gene categories (e.g.,  $\beta$ -lactamase resistance genes) and compared between intervention groups.

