## 13. Study assessments

The total study duration will be no more than 30 days of bedside assessments and no more than 6 months of telephone follow-up, both measured from the first recorded set of ICU vital signs. Samples will be gathered and bedside assessments made at the following intervals after ICU admission or until hospital discharge/death: baseline, 3 days, 7 days, 14 days, and 30 days. During study assessments, data will be combined from the following sources: (1) samples collected by the study team, (2) bedside assessments, and (3) data from the EMR.

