### 13.3.1. Tolerability

Patients who are alert will be asked regarding abdominal bloating which will be graded on a 4-point Likert scale (0=none, 1=a little, 2=a moderate amount, 3=a lot/severe). When patients are not alert, this will be graded as “unable.” ICU nurses will be asked to grade the average consistency of stools within each preceding 24 hours on a 5-point scale (0=like water, 1=like porridge, 2=loose but with chunks, 3=formed, soft, 4=formed, hard). This information will also be recorded from the EMR into REDCap as a separate entry. When subjects have no stools within the preceding 24 hours, this will be recorded as “no stools.” The frequency of stools within the preceding 24 hours will be recorded as an integer at each study assessment. Again, this will be done based both on the nurse’s in-person report and separately based on EMR documentation.

ICU nurses will be additionally asked regarding the presence or absence of the following symptoms during the 24 hour period prior to each study assessment: nausea, vomiting, bowel obstruction, and abdominal pain. This data will be recorded categorically on the CRFs/REDCap and will appear on DSMO reports.

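### Section 15 lists each patient's mean and maximum stool-consistency score; on this scale the maximum is the firmest score, so the loosest is not listed and cannot always be worked out

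*Combined protocol and SAP*

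**What the plan says.** Section 13.3.1 defines the measure: "ICU nurses will be asked to grade the average consistency of stools within each preceding 24 hours on a 5-point scale", with the anchors "0=like water, 1=like porridge, 2=loose but with chunks, 3=formed, soft, 4=formed, hard". A higher score is a firmer stool. A 24-hour window without stool is recorded as such and gives no score. Section 10.3.2 makes this a pre-specified adverse event: "Stool consistency, measured by subject or nursing report as an ordinal variable (0-4) over the 24 hours preceding each assessment". It compares such events between arms over two periods, one to ICU Day 7 and one to Day 30 or discharge.

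Section 15 sets out what the monitoring committee's reports will contain. For stool, the summary is "graded 0-4 for consistency and with an integer denoting frequency over 24 hours based on nursing report. For each patient, mean and maximum values". For bloating it is "Bloating: graded 0-3 based on patient report: patient mean and maximum values will be reported". For electrolytes, "For each patient, the minimum and maximum values for serum calcium, magnesium, phosphate, potassium, and sodium will be reported", and "This will be done for the 7 days of the intervention period and separately from Day 7 through Day 30/discharge". No such split is stated in the stool item.

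Section 13 schedules assessments at "baseline, 3 days, 7 days, 14 days, and 30 days", and section 9.2.1 adds one on the day of discharge for patients who leave hospital before Day 14. Nothing in the supplied document reverses the consistency scale or lists a minimum for it.

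**The concern.** Bloating and stool frequency both rise in the symptomatic direction, so a maximum picks out the patient's worst value. Consistency carries the same summary, but its loose end is at zero. The only extreme listed is therefore the firmest score. Yet section 6.1 counts diarrhea among the signs of fiber intolerance, and the product under test is a fermentable fiber.

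What is at stake is how clearly one tolerability signal shows in the safety report. A patient with a single watery score can appear in the listed summary exactly like a patient who never had one.

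**Working it through.** The plan gives no figure to reproduce. The check is whether the mean and maximum determine the minimum.

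**Inputs.** Integer scores 0 to 4 (section 13.3.1); mean and maximum per patient (section 15). The scheduled assessments allow at most five scores with baseline and four without. A discharge assessment before Day 14 replaces later visits, so it does not raise these ceilings.

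**One or two scores.** With one score the minimum equals the maximum. With two, minimum = 2 × mean − maximum, so it is always recoverable. Both statements need the number of scores to be known. Section 15 does not list it, and windows without stool make it vary. A mean of 3 with a maximum of 4 fits 2, 4 (6/2 = 3) and also 1, 4, 4 (9/3 = 3).

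**Three or more scores.** For n scores with maximum m, the sum can take every value from m to n × m, which is (n − 1) × m + 1 values. Summing over m = 0 to 4 gives 10 × (n − 1) + 5 possible (mean, maximum) pairs: 15, 25, 35 and 45 for n = 2, 3, 4 and 5. All unordered score sets were enumerated and grouped by pair. A pair is undetermined if it fits more than one answer.

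| Scores | Pairs | Minimum undetermined | Ever 0 undetermined | Ever 2 or less undetermined |
|---|---|---|---|---|
| 2 | 15 | 0 | 0 | 0 |
| 3 | 25 | 9 (36%) | 6 (24%) | 1 (4%) |
| 4 | 35 | 15 (43%) | 12 (34%) | 2 (6%) |
| 5 | 45 | 21 (47%) | 18 (40%) | 3 (7%) |

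Examples:
- 0, 4, 4 and 2, 2, 4 both have mean 8/3 = 2.67 and maximum 4. The minimum is 0 in one and 2 in the other.
- 1, 4, 4, 4 and 3, 3, 3, 4 both have mean 13/4 = 3.25 and maximum 4. The second patient never scored below 3.

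**How far this depends on the score distribution.** The documents give none, so the following rests on assumed, independent scores with the number of scores known. The probability that the minimum is undetermined with three, four and five scores is:
- mostly firm (probabilities 0.05, 0.10, 0.15, 0.40, 0.30 for scores 0 to 4): 68%, 87%, 95%
- centered (0.10, 0.20, 0.40, 0.20, 0.10): 65%, 82%, 91%
- mostly loose (0.30, 0.40, 0.15, 0.10, 0.05): 32%, 38%, 41%

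The range is too wide to quote a single rate, and it concerns the exact minimum only.

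**When three scores can arise.** If baseline is pooled in, baseline, Day 3 and Day 7 give three by Day 7. Without baseline, the Day 7 period has at most two scheduled scores. A third then arises only in the period through Day 30 or discharge: at Day 14, or at the discharge assessment for a patient who leaves between Day 7 and Day 14.

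**The case against.** The strongest reply is that little is lost.

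- **The data exist.** Every score is recorded, from the nurse and separately from the medical record, and section 10.3.2 does not restrict how consistency is compared between arms. This stands: the gap is in the listed summary, not in data collection.
- **Other summaries carry the signal.** Mean consistency and mean and maximum frequency are listed, and a sustained shift toward loose stool would lower the mean. This stands in large part. It does not cover an isolated watery score, which need not come with high frequency.
- **Baseline may not count.** Section 15 reports events in patients who received at least one dose, so a pre-dose score is arguably outside it. The Day 7 period then holds at most two scores and loses nothing if their number is shown. This stands for that period, but not for the one through Day 30 or discharge.
- **The list may not be exhaustive.** Section 15 does not say that only the mean and maximum will appear, and section 15.2 leaves further reporting detail to the DSMP, which was not supplied. This cannot be settled from the document.
- **The firm end may matter too.** Bowel obstruction is also a pre-specified event. This is a reason to keep the maximum, not to leave out the minimum.

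A reader might infer that the committee will be unable to see diarrhea, or that loose stool will usually go undetected. The documents do not support that. Whether a patient ever scored 2 or less is ambiguous in only 4 to 7% of possible pairs with three to five scores, and the other stool summaries remain.

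**Conclusion.** The point holds as a small gap in the safety-report specification. The stool item lists the firm extreme of consistency and not the loose one, although the same section lists both extremes for electrolytes. With three or more scores the listed values can leave the minimum undetermined, and with fewer they can do so when the number of scores is not shown. What can be hidden is mainly an isolated watery score.

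This rests on the section 13.3.1 scale being used unreversed and on the report containing what section 15 lists and no more. The table counts possible patterns; it does not say how many patients would be affected.

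It would be wrong to infer any effect on the trial's conclusions or on stopping. The primary outcome is the change in SCFA producers, the secondary outcome is MDRO colonization, and the boundary in section 17.4 counts toxicities; none is stated to use this summary. Severity: minor.

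**What to change.** In the stool item of section 15, report each patient's minimum consistency score alongside the mean and maximum, together with the number of scores, for the two periods in section 10.3.2. Keep the maximum. The same phrase can say whether the baseline score is included. If the DSMP already lists the minimum, a reference to it in section 15 is enough.

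The cost is one or two extra columns in the safety report and one phrase in the protocol, with no new data and no change to the case report form. The minimum will still describe only the 24-hour windows before the assessments.

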### 15.1. Serious adverse events

Federal Regulation 62 Oct. 7, 1997 defines SAEs as those events occurring at any dose which:

- Result in death;
- Are life-threatening, meaning the patient was at risk for death at the time of the event;
- Require hospitalization or prolong hospitalization;
- Results in significant disability or incapacity;
- Is a congenital abnormality/birth defect;
- Or does not meet these criteria but is thought by the investigator to be unusual and potentially serious.

SAEs in this trial will be AEs meeting the above Fed. Reg. 62 definition.

### **15.2. Adjudicating and reporting adverse events as unanticipated problems**

Unanticipated problems (UPs) will be any unforeseen medical event thought likely related to the study intervention. Such events will be monitored for in real time. UPs that do not meet criteria for seriousness (same as SAE criteria) will be reported to the DSMO and IRB at pre-specified intervals. UPs that meet criteria for seriousness will be reported within 24 hours from our notification of the event. This reporting will include:

- Contact of the DSMO;
- Contact of the Columbia IRB;
- Fax or email scan containing when the event occurred, the name of the reporter, callback information, the protocol number, and a description of the event;
- Availability of the PI to provide follow-up information regarding the event.

The proposed research is pending review by the Columbia University IRB (IRB #AAAS2576) and will be reviewed by the U.S. Army Medical Research and Materiel Command (USAMRMC) Office of Research Protections (ORP), Human Research Protection Office (HRPO) prior to implementation. Prior to initiation of research, the study will be registered on [clinicaltrials.gov](http://clinicaltrials.gov).

Safety and adverse effects will be overseen by the PI in conjunction with the Data and Safety Monitoring Officer (DSMO). **[name]**, the Director of the Medical Intensive Care Units at our institution will serve as the trial DSMO and will convene an appropriate Data and Safety Monitoring Committee (DSMC) to oversee interim study results. The primary responsibility of the DSMC will be to review interim data in terms of safety and make recommendations whether the study should be changed, halted, or terminated. Full details of the DSMC procedures and processes as well as additional details regarding AE and SAE reporting are in the DSMP.

#### **15.2.1. Compliance statement regarding research monitoring**

The DSMB under [name] will function as a **Research Monitor** and is responsible to oversee the safety of the research and report observations/findings to the IRB or a designated institutional official. The Research Monitor will review all unanticipated problems involving risks to subjects or others associated with the protocol and provide an independent report of the event to the IRB. The Research Monitor may discuss the research protocol with the investigators; shall have authority to stop a research protocol in progress, remove individual human subjects from a research protocol, and take whatever steps are necessary to protect the safety and well-being of human subjects until the IRB can assess the monitor's report; and shall have the responsibility to promptly report their observations and findings to the IRB or other designated official and the HRPO.

### **15.3. Unblinding for adverse events**

All possible efforts will be made to retain blinding for the duration of the trial. However, if a treating clinician feels that blinding must be removed in order to assess a possible adverse reaction quickly and correctly, the PI will facilitate this process by working through the DCC.

